11 QUALITY CONTROL AND QUALITY ASSURANCE

11.1 Study Monitoring

The study will be initiated by the Sponsor during an on-site visit after all required study documents have been sent to the Sponsor and approved. A monitor will perform

subsequent on-site monitoring visits as frequently as deemed necessary. At these visits, the monitor will compare the data entered onto the CRFs with the hospital or clinic records (source documents) and check for protocol compliance, including a review of records of informed consent, all subject visit dates, all AEs, all concomitant medications, and key efficacy observations. In addition, drug accountability records will be reviewed and findings from this review will be discussed with the Investigator.

The Sponsor expects that during monitoring visits, the study coordinator, Investigator, CRFs and source documentation will be available and a suitable environment will be provided for review of study-related documents.

11.2 Audits and Inspections

Trial sites, facilities, laboratories and all data (including sources) and documentation must be available for GCP audit by the Sponsor or inspection by competent authorities. Any aspect of the trial may be subject to audit by the Sponsor and/or inspection by regulatory authorities or the IRB. Such audits/inspections may take place at the Sponsor's site(s) or at the trial site including laboratories, pharmacies etc. In case of audit, the monitor will announce this in advance to the Investigator (or representative) and be present at the particular trial site during the audit.

The site staff should assist in all aspects of audit/inspection.

11.3 Data Quality Assurance

The Sponsor and their designated Contract Research Organization (CRO) will implement a system of quality assurance, including all elements described in this protocol. Within this system the CRO SOPs will be implemented to ensure that the clinical trial is conducted in compliance with regulatory requirements and GCP. Quality control is applied to each stage of data handling to ensure that data are accurate, reliable and processed correctly.

12 ETHICS AND ADMINISTRATIVE ISSUES

12.1 Ethical conduct of the trial

This protocol was designed and will be conducted, recorded and reported in compliance with the principles of Good Clinical Practice (GCP) regulations and in accordance with the principles outlined in the Declaration of Helsinki. These requirements are stated in federal regulations as well as ICH of Technical Requirements for Registration of Pharmaceuticals for Human Use, "E6 Guideline for Good Clinical Practice". The Sponsor representative will review these obligations with the Investigator prior to the initiation and throughout the course of the study. The Investigator or any of his or her staff should contact the Sponsor representative for any questions or issues regarding compliance with GCP/ICH guidelines.

This study will be conducted in compliance with IRB guidelines and in accordance with applicable regulations regarding clinical safety data management. In addition this study will adhere to all local regulatory requirements and requirements for data protection.

The Investigator should refer to 21 CFR Part 312, Subpart D, ICH Guidelines E6 for clarification of the Investigator's responsibilities for fulfillment of GCP Guidelines for Investigator's qualifications and agreements, adequate resources, medical care of study subjects, communication with IRB, compliance with the protocol, responsibility for investigational products, randomization procedures, informed consent, records and reporting, premature termination or suspension of a study and final reports.

Before initiating the study, the Investigator/institution must have written and dated approval/favorable opinion from the IRB for the study protocol/amendment(s), written informed consent form, any consent form updates, subject recruitment procedures (e.g. advertisements), and any written information to be provided to subjects, and a statement from the IRB that they comply with GCP requirements. The IRB approval must identify the protocol version as well as the documents reviewed.

12.2 Institutional review board/independent ethics committee (IRB/IEC) and Regulatory Authority

All protocols and protocol amendments must be signed and dated by the Investigator and approved by the IRB prior to implementation. The Investigator must provide an annual report to the IRB on the progress of the study in compliance with 21 CFR Part 56 and the IRB's policies and procedures. The Investigator must provide notification to the IRB of the completion, termination or discontinuation the study. It is required that a yearly review of the protocol by the IRB be documented in a letter from the IRB.

12.3 Subject informed consent

Executed informed consent, and other locally required documents such as those related to Protected Health Information, are required. The consent form must be executed prior to performing any study-related activities that are not part of the subject's routine care. The consent form that is used must be approved by both the reviewing IRB and by the Sponsor representative.

12.4 Subject Data Protection

Each subject must provide written informed consent as well as any authorizations required by local law (e.g. authorizations related to Protected Health Information). The Investigator agrees not to use or disclose Protected Health Information other than as permitted or required by the subject authorization or as required by law.

12.5 Data Monitoring Committee

Not applicable.

12.6 Financial Disclosure

Study personnel on the Form FDA 1572 will complete a financial disclosure form at the beginning of the study. New study personnel added to Form FDA 1572 must also meet these requirements.

12.7 Investigator Obligations

The Investigator should refer to 21 CFR Part 312, Subpart D, ICH Guidelines E6 for clarification of the Investigator's responsibilities to fulfill GCP Guidelines for Investigator's qualifications and agreements, adequate resources, medical care of study subjects, communication with IRB, compliance with the protocol, responsibility for investigational products, randomization procedures, informed consent, records and reporting, premature termination or suspension of a study and final reports.

The Investigator agrees when signing the protocol to adhere to the instructions and procedures described in it, and thereby, to adhere to the principles of GCP that it conforms to.

12.8 Changes to the Protocol

All protocols and protocol amendments must be signed and dated by the Investigator and approved by the IRB prior to implementation.

12.9 Confidentiality/Publication of the Study

All information supplied to the Investigator by a Sponsor representative and not previously published is considered confidential and remains the sole property of the Sponsor. The Investigator must agree to use this information only to accomplish this study, and must not use it for other purposes without the Sponsor's written consent. The information developed in this study will be used by the Sponsor in connection with

the continued developed in this study will be used by the Sponsor in connection with the continued development of this product and thus may be disclosed as required to other clinical Investigators or government regulatory agencies. To permit the information derived from the clinical studies to be used, the Investigator is obligated to provide the Sponsor with all data obtained in the study.

No publication of any study data, results, other deliverables or records is permitted by the Investigator.

12.10 Discontinuation of entire study

The Sponsor reserves the right to temporarily suspend or prematurely discontinue this study either at a single site or at all sites at any time for reasons including, but not limited to, safety or ethical issues or severe non-compliance.

In particular cases, the study may be terminated at a single investigational site, if the Sponsor has relevant reasons, e.g., suspicion of a deceit or conduct of the study which is not in accordance to the guidelines for GCP.

If the Sponsor determines such action is needed, the Sponsor will discuss this with the Investigator (including the reasons for taking such action) at that time. When feasible, the Sponsor will provide advance notification to the Investigator of the impending action prior to it taking effect.

The Sponsor will promptly inform all other Investigators and/or institutions conducting the study if the study is suspended or terminated for safety reasons, and will also inform the regulatory authorities of the suspension or termination of the study and the reason(s) for the action. If required by applicable regulations, the investigator must inform the Ethics Committee promptly and provide the reason for the suspension or termination.

13 DATA HANDLING AND RECORD KEEPING

13.1 Inspection of Records

Local regulatory agencies may request access to all study records, including source documents, for inspection and copying, in keeping with U.S. regulations. The Investigator should immediately notify the Sponsor of any upcoming regulatory agency inspections. The Sponsor may also perform an audit of the data if deemed necessary. The Investigator will be responsible for the accuracy of the data entered in the CRFs. The Investigator will permit designated Sponsor representatives and regulatory bodies to have direct access to the source documents to verify data represented in the CRFs.

13.2 Retention of Records

All source documents (e.g. informed consent forms, laboratory reports, progress notes, medical histories, physical and diagnostic findings, diagnosis and pharmacy records, and study drug dispensing/disposition records) that support data in the CRFs of each study subject must be retained in the files of the Investigator for at least two years after the last approval of a marketing application in an ICH region and until there are no pending or contemplated marketing applications in an ICH region; or at least two years have elapsed since the formal discontinuation of clinical development of the investigational drug. These documents should be retained for a longer period, however, if required by applicable regulatory requirements.

If the Investigator retires, relocates, or for any other reason withdraws from the responsibility of keeping the study records, custody must be transferred to a person who will accept the responsibility. Prior to transfer, the Sponsor representative must be notified in writing of the name and address of the new custodian.

1. INTRODUCTION

This Statistical Analysis Plan (SAP) describes the planned analyses and reporting for the clinical trial protocol CPC-001-12, sponsored by Chase Pharmaceutical Corporation. The reader of this SAP is encouraged to review the complete protocol, as this plan contains only a limited overview of protocol information. The main objective of the plan is to provide details pertaining to statistical methodology, data conventions, and processes used for the analysis of data from this trial.

The format and content of this SAP are structured to provide sufficient detail to meet the requirements specified by the International Conference on Harmonization (ICH) E9: Guidance on Statistical Principles in Clinical Trials. All analyses planned and presented in this SAP will follow the ethical guidelines published by the American Statistical Association (ASA).

The following documents were reviewed in preparation of this Statistical Analysis Plan:

- Version 3.0, protocol, July 22, 2016
- Guidance for Industry Adaptive Design Clinical Trials for Drugs and Biologics (2010)
- ASA Ethical Guidelines for Statistical Practice (2016)
- The Royal Statistical Society: Code of Conduct (2014)
- ICH Guidance on the Structure and Content of Clinical Study Reports (ICH E3, 1996)
- ICH Guidance on the Statistical Principles for Clinical Trials (ICH E9, 1998)

2. PROTOCOL DESIGN

2.1 Design Overview

This is a Phase II, ascending dose study of CPC-201 in patients with dementia of Alzheimer's type to determine the optimal dose titration schedule. The study involves a step wise cohort design in two different patient populations: Group 1 will consist of patients who have been treated with donepezil 5 or 10 mg/day (given once daily) for at least 4 weeks just prior to Day1. Group 2 will consist of patients who have never been treated with donepezil before (donepezil naïve) or who have not received any other

AChEI for the past 6 months.

Original Plan

Donepezil dose will be increased at weekly intervals, in accordance with the schedules given below, to its first intolerable dose (FID) or maximum allowed dose (MAD) 60 mg/day together with solifenacin 15 mg/day. If a patient does not tolerate a donepezil dose higher than 40mg/day with solifenacin 15 mg/day, the solifenacin dose can be increased to 20mg/day per the Investigator's decision.

Cohort 1	1 st week: 20mg donepezil + 15mg solifenacin 2 nd week: 30mg donepezil + 15mg solifenacin 3 rd week: 40mg donepezil + 15mg solifenacin 4 th week: 50mg donepezil + 15mg (or 20mg) solifenacin 5 th week: 60mg donepezil + 15mg (or 20mg) solifenacin
Cohort 2*	1 st week: 20mg donepezil + 15mg solifenacin 2 nd week: 40mg donepezil + 15mg solifenacin 3 rd week: 60mg donepezil + 15mg (or 20mg) solifenacin
Cohort 3*	1 st week: 20mg donepezil + 15mg solifenacin 2 nd week: 60mg donepezil + 15mg (or 20mg) solifenacin

*: The dose titration schedule of Cohort 2 and 3 may be altered based on Cohort 1 result.

Patients reaching their FID or having completed one week treatment with MAD, have two options.

Option 1: Patient will be allowed to immediately enter a long term extension at their maximum tolerated dose (MTD) or MAD.

Option 2: Patients may choose not to enter the long term extension, in which case the Investigator will decide whether the patient should discontinue high dose of donepezil without down-titration, or whether donepezil should be dwn-titrated to their own standard of donepezil dose. Whatever the decision, the patient will be treated at least an additional 7 days with solifenacin 15 mg/day.

First Amendment

After 8 subjects in Cohort 1 and 1 subject in Cohort 2 were enrolled, the protocol was amended to add Cohort 1b and to limit to enroll only Group 1.

Patients currently treated with donepezil (Group 1) will receive solifenacin 15 mg/day
20170802_Chase_CPC-001-12_SAP_Final Version 1.0.docx Confidential

during a two week run in period; donepezil treatment will continue at 10mg/day. Once on 15 mg/day of solifenacin for two weeks (based upon the investigator judgment), the donepezil dose will be increased at weekly or bi-weekly intervals, in accordance with the schedules given below, to its first intolerable dose (FID) or maximum allowed dose (MAD) of 60mg/day

Cohort 1b	1st-2nd week: 10mg donepezil + 15mg solifenacin 3rd week: 20mg donepezil + 15mg solifenacin 4th week: 30mg donepezil + 15mg solifenacin 5th week: 40mg donepezil + 15mg solifenacin 6th week: 50mg donepezil + 15mg (or 20mg) solifenacin 7th week: 60mg donepezil + 15mg (or 20mg) solifenacin
-----------	--

Second Amendment

[figure not shown]
After 6 subjects were enrolled in Cohort 1b, the protocol was amended to add Cohort 3c.

All subjects entering the study in cohort 3 will start with a dose regimen of 10mg donepezil + 15mg solifenacin and will continue to increase the donepezil dose by 5mg increments every 7 days (or up to 14 days per PI discretion) up to 40mg or the MTD.

Cohort 3c	1st week: 10mg donepezil + 15mg solifenacin 2nd week: 15mg donepezil + 15mg solifenacin 3rd week: 20mg donepezil + 15mg solifenacin 4th week: 25mg donepezil + 15mg solifenacin 5th week: 30mg donepezil + 15mg solifenacin 6th week: 35mg donepezil + 15mg solifenacin 7th week: 40mg donepezil + 15mg solifenacin
-----------	---

All the schedule of assessments for this study are presented in the protocol and also in the Appendix 1 of this SAP.

2.2 Clinical Trial Treatments

2.2.2 Randomization and Blinding

This is a single-blind dose escalating open label study. The subject, caregiver, and site personnel who assess MMSE and ADAS-Cog are blinded.

2.3 Protocol Objective(s)

2.3.1 Primary Objective

To determine the optimal initial dose and subsequent dose titration schedule (rate and increment) for CPC-201.

2.3.2 Secondary Objectives

To evaluate the safety and tolerability of CPC-201 as a function of dose and initial rate of dose titration.

2.4 Study Outcome Measures

2.4.1 Primary Outcome Measure

The primary outcome for this study is optimal initial dose and subsequent dose titration schedule (rate and increment) for CPC-201.

- The FID of each patient
- The MTD of each patient

2.4.2 Secondary Outcome Measures

2.4.2.1 Safety Assessments

Safety will also be evaluated on:

- Dose limiting side effects
- AEs and SAEs (type, severity, and frequency),
- vital signs (systolic and diastolic blood pressure; radial artery pulse rate; body weight),
- 12-lead ECG,
- Safety lab,
- Physical examination, and
- Suicidality modified C-SSRS.

[REDACTED]

[REDACTED]

- [REDACTED]
- [REDACTED]

[REDACTED]

- [REDACTED]

- [REDACTED]

3. SAMPLE SIZE DETERMINATION

No formal sample size calculation has been made. Based on experience from previous similar studies, a total 4-6 evaluable subject per group per cohort is considered sufficient.

4. INTERIM ANALYSIS/DSMB

No Interim Analysis (IA) was planned to be conducted.

5. HYPOTHESIS TO BE TESTED

There is no formal hypothesis testing for this study. The study is not powered to reliably yield statistically significant conclusions.

6. ANALYSIS POPULATIONS

6.1 Safety Population

The Safety population is defined as all subjects those who received at least one dose of any study drug. This population will be used for analysis of safety parameters.

6.2 MTD (Maximum Tolerable Dose) Evaluable population

The MTD evaluable population is defined as all subjects who completed the donepezil dose titration. This population will be used for summary of the primary study outcome.

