3.5.2 Discontinuation of individual subjects from the entire study

During the study, the investigator or the sponsor may decide to discontinue a subject's participation in the study in the following cases:

- A protocol violation occurs;
- A serious or intolerable (other than those listed in the discontinuation of rivastigmine escalation criteria) AE occurs;
- The Sponsor or Investigator terminates the study.
- The subject requests to be discontinued from the study.
- The subject is non-compliant to any part of the study.
- The Investigator feels it is not in the best interest of the subject to continue in the study.

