7.3 Assessment of tolerability

The FID of each patient will be recorded.

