7.3 Handling of Missing Data

All data will be used as observed, and no imputations will be made for any missing data point. All summaries will be based on observed data only.

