8.2 Analysis Primary Outcome Measure

The primary outcome measure for the study is the optimal initial dose and subsequent dose titration schedule of donepezil when given with solifenacin (15 mg/day or 20 mg/day).

Time to reach FID (First Intolerable Dose) for each patient will be presented as a subject specific listing. The proportion of subjects at the different MTD levels and those who were able to tolerate the highest dose of donepezil (i.e., 40 mg/day) and the MTD will be summarized descriptively. In addition, descriptive summary (i.e., n, mean, SD) of the highest dose reached will be presented.

The dose limiting side effect will be listed.

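### SAP 6.2 limits the primary-outcome summary to subjects who completed titration but does not define completion, so the top-dose proportion rests on an unstated classification and an inconsistent reference dose

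*SAP*

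**What the plan says.** **Analysis set.** SAP 6.2 states: "The MTD evaluable population is defined as all subjects who completed the donepezil dose titration". It assigns this set to the summary of the primary outcome. The Safety population in SAP 6.1 is wider: "all subjects those who received at least one dose of any study drug".

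**What is summarised.** SAP 8.2 plans the proportions at each MTD level, the proportion of "those who were able to tolerate the highest dose of donepezil (i.e., 40 mg/day"), and a "descriptive summary (i.e., n, mean, SD) of the highest dose reached will be presented". It names no population. Protocol 9.1.1 plans MTD and FID statistics for every patient within each titration schedule, and SAP 2.4.1 also lists both measures per patient.

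**When titration ends.** SAP 2.1 says: "Patients reaching their FID or having completed one week treatment with MAD, have two options". Protocol 3.1 matches this, with a MAD of 60 mg/day, or 40 mg/day in Cohort 3c. Protocol 3.2 describes subjects who meet a stopping rule as withdrawn from titration and sends them to the same two options. Its last rule is a catch-all left to the investigator's opinion. SAP 8.1.1 counts subjects who completed titration separately from those who discontinued before completing it.

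**Leaving the study.** Protocol 3.5.2 allows removal from the whole study when "A serious or intolerable (other than those listed in the discontinuation of rivastigmine escalation criteria) AE occurs". Rivastigmine is not a study drug here.

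**Recording and missing data.** Protocol 7.3 says "The FID of each patient will be recorded". SAP 7.3 says "no imputations will be made for any missing data point".

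**The concern.** Membership of the primary analysis set depends on how far a subject got in titration, and that is largely the outcome being measured. A subject who leaves because the drug was not tolerated is informative about tolerability. If such a subject falls outside the set, the denominator shrinks and the proportion tolerating the cohort's top dose rises. The highest dose reached would be lost too, although it is known for everyone who was dosed.

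The term that decides membership is undefined in the visible text, and the passages pull in different directions. SAP 2.1 and protocol 3.1 suggest that titration ends at the FID or after a week at the MAD. Protocol 3.2 and SAP 8.1.1 allow a programmer to class a stopped subject as withdrawn or discontinued, and so not a completer.

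Protocol section 9 says that the descriptive results are meant to guide the design of later trials, so the denominator behind the main proportion should be explicit.

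**Working it through.** **1. No planned figure to reproduce.** SAP 3 and 5 give no formal sample size calculation and no hypothesis test. SAP 3 considers 4-6 evaluable subjects per group per cohort sufficient. The check is therefore a comparison of denominators.

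**2. Inputs.** SAP 2.1 reports 8 subjects enrolled in Cohort 1, 1 in Cohort 2 and 6 in Cohort 1b when the amendments were made. The number *k* tolerating the cohort's top dose and the number of exits *e* are not in the documents. Both are assumptions and *k* is varied.

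**3. Reading A: reaching the FID or the MAD is completion.** Subjects stopped by the escalation rules stay in. An adverse-event exit with no FID recorded drops out. All treated: k/n. Completers: k/(n - e). For e = 1, with an exit who did not tolerate the top dose, the rise is k/[n(n - 1)].

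| n | k | All treated | Completers | Rise (points) |
|---|---|---|---|---|
| 6 | 1 | 16.7% | 20.0% | 3.3 |
| 6 | 3 | 50.0% | 60.0% | 10.0 |
| 6 | 5 | 83.3% | 100% | 16.7 |
| 8 | 1 | 12.5% | 14.3% | 1.8 |
| 8 | 4 | 50.0% | 57.1% | 7.1 |
| 8 | 7 | 87.5% | 100% | 12.5 |

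With e = 2, n = 6 and k = 3, the proportion is 3/4 = 75.0%. With e = 0 there is no change. In Cohort 2, with n = 1, one exit leaves nobody evaluable.

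**4. Reading B: only finishing the week at the MAD is completion.** FID subjects drop out as well. The completers are then exactly the *k* subjects, so k/k = 100% for any k > 0. An assumed 3/6 = 50% would be shown as 3/3 = 100%.

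**5. Highest dose reached, if SAP 6.2 governs it.** Dropping one subject shifts the mean by (mean of the rest - that subject's value)/n. With assumed highest doses of 20, 30, 40, 60, 60 and 60 mg, the mean is 270/6 = 45.0. Without the 20 mg subject it is 250/5 = 50.0. The shift is (50 - 20)/6 = 5.0 mg. It is zero if the exit's value equals the mean of the rest.

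**6. Reference dose.** SAP 8.2 equates the highest dose with 40 mg/day. SAP 2.1 sets the MAD at 60 mg/day for Cohorts 1, 2 and 1b. Suppose 40 mg/day is the criterion in a 60 mg/day cohort, and a subject who tolerated 40 mg exits at 50 mg with no FID. A success is then lost: 3/6 = 50.0% becomes 2/5 = 40.0%, or 4/8 = 50.0% becomes 3/7 = 42.9%. The direction under Reading A is therefore not fixed until the reference dose is settled.

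**The case against.** The affected class under Reading A may be empty. The catch-all in protocol 3.2 can turn most adverse-event exits into an escalation stop with an FID, and protocol 7.3 says without exception that each patient's FID is recorded. Where protocol 3.1 gates enrolment on completed titration, its wording fits an end at the FID or the MAD. Exits remain visible in the disposition table with reasons, in the listings, and in the Safety-population tolerability analyses of SAP 8.3.1, and in cohorts this small a reader can find each one. The study is descriptive, and an assumed 3/6 has an exact 95% interval of 11.8% to 88.2%, so a 10-point shift is small beside sampling error. SAP 8.2 names no population, so applying 6.2 to the highest dose reached is an inference.

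Most of this stands as a limit on size. In particular, a reader might infer that nothing in the plan requires an FID at a study exit. The documents do not support that: protocol 7.3 is unqualified, and the visit procedures and SAP Appendix 1 are not shown.

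Three things remain:
- A patient who tolerates the MAD has no FID, so protocol 7.3 cannot be literal for everyone, and no visible rule assigns an FID at an exit under 3.5.2.
- Reporting an exit in another table does not correct the denominator of the primary one.
- None of these arguments settles Reading A against Reading B, or the 40 versus 60 mg/day mismatch.

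**Conclusion.** The point holds as a gap in definition with a conditional effect on a descriptive proportion. SAP 6.2 narrows the per-patient summary of protocol 9.1.1, gives no visible reason, and rests on an undefined term. On the better-supported Reading A, the effect is zero with no exits lacking an FID. With one such exit below the top dose it is about 2 to 17 points at the enrolled sizes of 6 and 8. On Reading B the top-dose proportion carries no information. Separately, the reference dose in SAP 8.2 conflicts with the MAD of three cohorts, whether or not anyone exits.

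A reader might go further and conclude that the plan discards intolerant subjects and that its result is inflated. The documents do not show this. No such exit is reported, subjects stopped by the escalation rules stay in under Reading A, the FID itself is only listed by subject, and the direction can reverse if 40 mg/day is the criterion in a 60 mg/day cohort. No error rate or power is at stake. The figures rest on assumed values of *k* and *e*, and on SAP 6.2 governing the summaries in 8.2.

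**What to change.** SAP wording only, with no dosing or stopping rule touched:

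1. In 6.2, state that reaching the FID or the MAD counts as completing titration for analysis, and bring protocol 3.2 and SAP 8.1.1 into line so that a stopped subject is classed one way throughout.
2. In 8.2, name the population. Summarise highest dose reached and the top-dose proportion by cohort in the Safety population. Keep exits before the FID or the MAD in the denominator and show them as their own category. For example, with 6 treated, 3 at the top dose, 2 at an FID and 1 early exit, report 50.0%, 33.3% and 16.7%. Keep the completer set as a sensitivity summary.
3. Reconcile the 40 mg/day in 8.2 with the cohort-specific MAD, and print the reference dose beside each cohort's proportion.

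Dosing, adverse-event and disposition data are already collected, so the cost is a few more table rows. The top-dose proportion may look less favourable.
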